The study will use cross-over, randomized, sham controlled, double-blinded design in which 15 participants with subacute or chronic ABI will be assigned to receive either active anodal spinal stimulation, cathodal spinal stimulation, and sham spinal stimulation experiments for the same duration in a random order. In all the experiments participants will receive exoskeleton-assisted training for duration of 1.5 hours. The first 20 minutes of training will be coupled with spinal

stimulation. Treatment will be administered at an intensity of 5 sessions per week for 2 weeks (Please see study HSC-MS-15-0269 PI: [name]).

Pre-screening Procedures: During the pre-screening process, potential subjects with ABI will be contacted by phone from research personnel. The aim and details of the study will be explained in details (reading from a phone script) and information such as demographics, medical history, medications being used, etc. will be gathered. Also ABI subjects will be screened for tsDCS and transcranial magnetic stimulation (TMS) contraindications (attachment 1, attachment 2) and a subgroup of patients (n=5) will be screened for MRI contraindications (attachment 3). The pre-screening will last about 30 minutes and will be performed in a private area. Once this information is collected, the coordinator will consult with the Drs. [name] (PI) and [name] and they will give final approval for the subject to come to The Institute for Rehabilitation and Research Memorial Hermann for the screening procedure.

Screening (Visit 1, duration: One hour): After subject arrives at TIRR a research personnel will meet him/her at the Motor Recovery Laboratory. The details of the study-specific procedures will be reviewed with the subject together. Subject will be screened for inclusion and exclusion criteria. Signed and dated informed consent will be obtained. Demographics, medical history, list of medications will be recorded. If the subject is female in child bearing ages, a urine pregnancy test will be requested. A medication diary will be given to the subject and asked to document all changes in type and dosage of the medication he/she has been using throughout the study. This will allow us to differentiate a potential effect of a change in dosage or type of medication on movement recovery. After subject meets all Inclusion and Exclusion Criteria he/she will be randomly assigned to active, cathodal or sham tsDCS group.

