Exoskeleton-assisted training: The side being trained (right vs left arm) will be weaker side of the body. Treatment will be provided by [name], in a dedicated therapy area in the UTHealth Motor Recovery Lab at TIRR-Memorial Hermann. Subjects will individually perform upper-extremity therapy exercises that are supported by the exoskeleton device. Activities that the subjects will be asked to perform will be selected based on the subject's upper-extremity motor function, including elbow flexion-extension, forearm pronation-supination, wrist flexion-extension, and radial-ulnar deviation. The tasks will be repeated multiple times per session for improved performance. Graphic feedback about performance will be given after each attempt in order to maintain motivation. Rest breaks will be given in order to avoid fatigue.

fNIRS: to measure brain activity over the treatment duration at the beginning of each session fNIRS system will be placed over the head of the subject. Brain activity will be recorded during rest (no active movement with the hand) and during movement (performing a motor task with hand).

Safety Assessment:

Questionnaire: At the end of each therapy session, tsDCS side effects questionnaire will be used to monitor any adverse events and study adherence (attachment 3). At the end of each session, the subject will describe any sensations they felt during stimulation and if they feel anything unexpected happened during the study visit. In addition the subject will be asked to rate his/her level of fatigue, pain, and satisfaction with the activities during the session.

Tolerability Assessment: Participants will be asked to rate the cervical spine unpleasantness and discomfort with a subject scale defining the level from “no discomfort at all” to “unbearable discomfort”.

Post-treatment and Follow-Up Assessment (Visit 13-15, duration: one and a half hours): During this period subjects will be asked to come within a-week after they have completed the study, at week-1 and month-1. Month-1 assessment will serve as the baseline assessment of the next treatment arm. Motor functions tests, exoskeleton measures and neurophysiological measurements with SSEP, TMS and fNIRS will be repeated after the treatment, at 1-week and at 3- months follow-up visits. MRI scan will be performed before and after treatment only.

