2- After subjects are identified by their treating physicians and therapists, they will be referred to the co-investigator. During this first contact, the researcher will briefly explain the study content and request their phone number and e-mail address to contact them later for a pre-screening. During a phone call, a brief pre-screening procedure will be applied. Demographics and medical information such as surgery implants, medications, psychiatric, drug and alcohol history as inclusion and exclusion criteria will be gathered. Drs. [name] and [name] will review the information gathered during phone screening and may request more information about the surgery such as type of surgical implants, previous MRI notes, etc. In our experience with previous projects, we always needed to collect information from patients' medical record before the person could be enrolled into the study. For example if a surgery had been performed an approval from surgeon's office was requested to confirm the compatibility of surgical instruments with 3Tesla MRI. In some circumstances we further confirmed the surgical implants' compatibility with the manufacturing company. After all information are gathered Drs. [name] and [name] will agree or decline subject's enrollment into the study. A copy of consent form will be e-mailed to subject.

3- Potential subjects will be invited to come for a screening visit to Motor Recovery Laboratory at TIRR Memorial Hermann. Any information gathered during phone screening will be stored in a locked file cabinet and password protected electronic file. During the screening visit, an investigator at TIRR will obtain informed consent. The test procedures will be described and the testing equipment will be shown to the subject. A co-investigator will clearly explain all the procedures and risks of the testing outlined in the consent form. The subject will be given sufficient time to consider their decision and will be encouraged to ask questions, both during the initial interview and throughout the study. The PI or a co-investigator will answer any questions regarding the study at the time consent is given. Once enrolled, the subject may pause or terminate his/her participation at any time during the study.

4- Alternatively any person with ABI who are living in the community and been informed through flyers can contact the researchers directly and request more information about the study.

7. DATA ANALYSIS:

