Data analysis: Analyses will be performed with two-tailed significance tests at the 95% confidence level and are planned using parametric methods with continuous variables.

However, before performing parametric analyses we will examine the data for evidence of assumption violations and, if such violations are serious, we will perform data transformations or use non-parametric methods as appropriate. Four comparisons will be made. The primary efficacy variable will be the change in hand functions as measured with Jebsen-Taylor Hand Function test. Secondary outcome measures include change in strength of selective muscle groups, change in movement function and number of subjects who will reach minimally clinical significant change (ARAT), and muscle tonus (Modified Ashworth Scale) and change in movement smoothness (exoskeleton measurements), and change in the neurophysiological responses of central nervous system (TMS, SSEP). Adverse effects will be monitored with a Side Effects Questionnaire.

Within subject comparison of after treatment vs. baseline will be performed, separately for each group, using paired t-test. Second, a between groups will examine the effects of treatment by using a repeated measures of ANOVA to test for a time x group interaction. Third subjects' ratings of pain and fatigue after each therapy session will be compared the pain and fatigue ratings, to determine if there was unacceptable to subjects.

The level of significance used will be $p < 0.05$.

Analysis for Neuroimaging scans: Biological correlates of the tsDCS and training will be obtained by computing white matter fiber integrity measures of the CST using diffusion tensor imaging an analysis in AFNI (Cox, 1996) and DTI Query (Sherbondy et al, 2005). Integrity measures will include fiber tract density, strength, and their interaction (Ellmore et al 2011), as well as a comparison of parallel and perpendicular diffusivities to investigate changes in axonal integrity and myelination, respectively. We specifically predict that tsDCS combined with repetitive training will result in increased white matter integrity, including increased fractional anisotropy, increased tract density, and changes in axial and radial diffusivities that are consistent with improved myelination and axonal coherence.

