Exoskeleton-training: Patients with acquired brain injury sometimes develop pain or discomfort in the shoulders and arm. In an ongoing study in our laboratory with subjects who are undergoing robotic-exoskeleton exoskeleton training for three- hours per session and three-sessions per week for four weeks, didn't show any significant fatigue, discomfort or pain lasting longer than 24 hours after training ([name] et al, 2012). If there is evidence that pain or

fatigue is worsened by the therapy, the sessions will be reduced or discontinued. All therapy sessions will be supervised by a project staff member. **Assessment/Questionnaires:** All assessments will be performed in a designated room inside Motor Recovery Laboratory. None of these tests are either painful or uncomfortable to perform. In order to prevent potential embarrassment during the testing the test will be done individually and in private. If subjects feel uncomfortable in answering any of the questions they may stop the study at any time.

9. POTENTIAL BENEFITS:

As with any study focusing on basic research, the subjects will derive no direct benefit. The results of these studies may benefit subsequent future subjects if combined spinal stimulation with repetitive training via a exoskeleton device proves to be effective when compared to cortical stimulation with repetitive training. We envision that in the near future the information obtained from the proposed research will provide a better understanding for treatment options of upper extremity motor function in acquired brain injury.

The benefits of participating in this study may be improved arm and hand movement. However, there may be no benefit from participating in this study.

10. RISK-BENEFIT RATIO:

The potential improvement of arm and hand movement outweighs the risk of non-invasive spine stimulation, fatigue, pain and discomfort.

11. CONSENT PROCEDURES:

Informed consent will be obtained from the subject at Motor Recovery Laboratory at The Institute for Rehabilitation and Research. After the patient is identified by the PI and her research team study criteria and he/she is interested in participating, informed, written consent will be obtained by a member of the research team.

In addition a photography/videotaping consent will be obtained from the subject, if he/she agrees to be photographed / videotaped during the assessments or treatment sessions.

12. CONFIDENTIALITY PROCEDURE:

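### Acceptability is judged only from ratings after sessions that were held, and stopping for pain or fatigue is not counted, so the comparison can lean towards 'acceptable'

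*Combined protocol and SAP*

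**What the plan says.** The design in Section 4 is a three-condition crossover: "15 participants with subacute or chronic ABI will be assigned to receive either active anodal spinal stimulation, cathodal spinal stimulation, and sham spinal stimulation". On frequency, "Treatment will be administered at an intensity of 5 sessions per week for 2 weeks", which makes 10 planned sessions per condition.

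Under Safety Assessment, Section 4 describes an end-of-session questionnaire: "In addition the subject will be asked to rate his/her level of fatigue, pain, and satisfaction with the activities during the session". The same paragraph says that a "tsDCS side effects questionnaire will be used to monitor any adverse events and study adherence".

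Section 7 uses the ratings in its third comparison: "ratings of pain and fatigue after each therapy session will be compared the pain and fatigue ratings, to determine if there was unacceptable to subjects". It does not say what the ratings are compared with, how they are summarised, what cut-off applies, or what happens when a rating is missing.

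Section 8, under Exoskeleton-training, states what follows if there is evidence that pain or "fatigue is worsened by the therapy, the sessions will be reduced or discontinued". Section 6 adds that "the subject may pause or terminate his/her participation at any time during the study".

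**The concern.** The quantity being rated can end its own measurement. A participant whose pain or fatigue worsens may have sessions withdrawn, and a session that is not held yields no rating. The ratings that go missing are those one would expect to be highest. The act of stopping, which is the plainest evidence that treatment was not acceptable to that person, is not part of the Section 7 comparison.

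A shortened session is still rated, but after less exposure, which also pulls the rating down. The crossover can add to this: someone who leaves during one condition may give no ratings in later ones, so a within-person comparison would rest on those who tolerated everything.

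What is at stake is a tolerability conclusion that could err in the reassuring direction. The efficacy analyses are not affected by this point. Supplying the missing comparator or a cut-off would not solve it, because the ratings would still be absent.

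**Working it through.** **Is there a figure to reproduce?** No. The documents give no stopping rate, rating scale, acceptability threshold, SD or summary measure for this comparison.

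**Counts.** Planned ratings per condition are 15 × 10 = 150. If, as an assumption, 3 of 15 stopped after session 3, the ratings obtained would be 12 × 10 + 3 × 3 = 129. Only 12 people would be rated at session 10, and the 21 missing ratings would all belong to the people who stopped.

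**Does another record fill the gap?** The questionnaire that monitors adherence is completed at the end of a session, so it cannot describe a session that was not held. Table 1 places adverse events at the assessment visits. Neither source is named in the Section 7 comparison.

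**Illustration of direction.** All inputs here are assumptions: a 0-10 scale, tolerant participants averaging 2, and no further ratings after the first one at or above a stop value. In the *moderate* case, k intolerant participants start at 3 and rise 0.5 per session, with SD 1. In the *steep* case they rise 1.2 per session from 2. I define

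signal lost = 1 − (observed − base) / (full − base),

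where base is the mean with nobody intolerant (2.01) and full is the mean had every session been rated.

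Moderate case, all sessions:

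| k of 15 | stop at | full | pooled ratings | lost | per-participant means | lost |
|---|---|---|---|---|---|---|
| 3 | 6 | 2.66 | 2.35 | 1 − 0.34/0.65 = 48% | 2.49 | 1 − 0.48/0.65 = 26% |
| 3 | 7 | 2.66 | 2.51 | 1 − 0.50/0.65 = 23% | 2.58 | 1 − 0.57/0.65 = 12% |
| 5 | 6 | 3.09 | 2.61 | 1 − 0.60/1.08 = 44% | 2.82 | 1 − 0.81/1.08 = 25% |
| 5 | 7 | 3.09 | 2.87 | 1 − 0.86/1.08 = 20% | 2.97 | 1 − 0.96/1.08 = 11% |

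Steep case, stop at 6, with 1, 2 or 3 of 15 stopped: the pooled difference from a condition with nobody intolerant is 0.07, 0.15 or 0.23, against 0.32, 0.64 or 0.96 with nothing lost. For two people, 1 − 0.15/0.64 = 77%; a re-run without rounding gave 75-77% across the three. With per-participant means the loss is about 54%.

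Last session, attenders only, moderate case, k = 3: the full mean is 3.11. With a stop at 6 the observed mean is 2.02, so the loss is 1 − 0.01/1.10 = 99%. With a stop at 7 it is 2.33, so the loss is 1 − 0.32/1.10 = 71%.

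The direction was the same in every scenario. The size depends on how steeply ratings rise, where people stop, and which summary is used.

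**Power of a within-person count.** For discordant pairs that all point one way, exact McNemar p = 2 × 0.5^n. Three against none gives 2 × 0.125 = 0.25; five against none gives 2 × 0.03125 = 0.0625.

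**The case against.** Several stronger readings are tempting, and the documents do not support them.

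- *A reader might infer that the less tolerable stimulation condition must lose more ratings.* The rule sits under exoskeleton training, which all three conditions share. Loss differs by condition only if stimulation itself changes pain or fatigue. Section 7 does not even say that this comparison is between conditions.
- *A reader might infer that any reduction ends the ratings, or that the worst values all go.* A shortened session is still held and rated, and the rating that reveals the worsening is kept.
- *A reader might infer that about three quarters of the signal disappears.* That figure needs the steep case, in which an intolerant participant's ratings would reach about 10 out of 10 by session 10 if all were obtained. It also needs pooled ratings, which under-weight people who stop early. Using each person's last obtained rating, the steep case still shows differences of about 0.34, 0.68 and 1.02. Near-total loss belongs to an attenders-only final-session contrast with a stop at 6, which the plan does not specify.
- *A reader might infer that such a participant vanishes.* The side-effects questionnaire, the discomfort scale and the adverse-event record would leave traces, though none feeds the comparison.

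Stopping may also be rare. Section 8 reports no significant fatigue, discomfort or pain beyond 24 hours in an ongoing study in the same laboratory with three-hour sessions. Nor is every shortening a sign of unacceptability, so scoring all reductions that way would be debatable.

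These objections limit the size and the wording. They leave the mechanism standing: ratings can be lost because of the outcome being rated, and Section 7 neither handles the loss nor counts the stop.

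**Conclusion.** The point holds as a possible bias towards 'acceptable', with its direction established and its size unknown. It follows from reading Sections 4, 7 and 8 together and does not depend on the simulated figures. Under the assumed inputs, with a stop at 6 or 7, the loss spans about 20-77% for pooled ratings and 11-54% for per-participant means. These figures show sensitivity to assumptions and do not estimate what would happen in this trial. If nobody is stopped or reduced for pain or fatigue, there is no bias. A difference in bias between conditions is conditional on an effect of stimulation on pain or fatigue. This is a secondary tolerability question in 15 people, but the remedy is cheap enough that it should be made.

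**What to change.** In Section 7:

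1. Add an acceptability outcome per participant and per condition, which counts discontinuation of sessions because of pain or fatigue as 'unacceptable'. The denominator is everyone who started that condition.
2. Report reduced or shortened sessions for pain or fatigue separately, by condition, with reasons from the session log.
3. Present these counts within person and mainly descriptively, because a test on so few discordant pairs says little.
4. If ratings are also compared, use all obtained ratings, name the summary measure, and add a sensitivity analysis that gives the worst rank to sessions not held because of pain or fatigue.

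The cost is revised wording and a reason field on the session log. No visits or participants are added. The acceptability result may look less favourable. The clinical rule in Section 8 is unchanged.
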